1.0 LIST OF ABBREVIATIONS

AA **Alcoholics Anonymous**

ΑE Adverse Event

ASI Addiction Severity Index CA Cocaine Anonymous

CBT Cognitive-Behavioral Therapy

CMA Crystal Meth Anonymous CoC Certificate of Confidentiality

CRF Case Report Form

CSAT Center for Substance Abuse Treatment

CSS Clinician and Supervisor Survey

CT Cognitive Therapy

CTN Clinical Trials Network

CTP **Community Treatment Program** DVA Department of Veterans Affairs

DSMB Data and Safety Monitoring Board

FWA Federal-Wide Assurance GCP **Good Clinical Practice** GDC Group Drug Counseling

HIPAA Health Insurance Portability and Accountability Act

ICH International Conference on Harmonization

IDC Individual Drug Counseling IOP Intensive Outpatient Program

IRB Institutional Review Board

ITT Intent to Treat

MATCH Matching Alcoholism Treatment to Client Heterogeneity

MET Motivational Enhancement Therapy

NA **Narcotics Anonymous**

NCCTS NIDA Cocaine Collaborative Treatment Study

NIDA National Institute on Drug Abuse OPT **Outpatient Psychosocial Treatment**

Ы Principal Investigator RA Research Assistant

SAE Serious Adverse Event

SE Supportive-Expressive Therapy

SECA Systematic Encouragement and Community Access

SEQ-P Self-efficacy Questionnaire – Patient version

SOCRATES Stages of Change Readiness and Treatment Eagerness Scale

STAGE-12 Stimulant Abuser Groups to Engage in 12-Step

SUD Substance Use Disorders

SUSS Short Understanding of Substance Abuse Scale

TAU Treatment-as-Usual

TSF Twelve-Step Facilitation Therapy

TSR Treatment Services Review

SHAQ Self-Help Activities Questionnaire

2.0 STUDY SYNOPSIS

STUDY OBJECTIVES: The primary objective of this protocol is to evaluate the degree to which a combined group and individual 12-Step facilitative intervention, Stimulant Abuser Groups to Engage in 12-Step (STAGE-12), improves substance-related outcomes compared to treatment as usual (TAU) without STAGE-12 among stimulant abusers. For this protocol, STAGE-12 will be integrated into treatment as usual. The primary objective is to evaluate reduction in percent of days of stimulant use as measured by self-report. Secondary objectives include evaluating reduction in percent days of use of other substances, the degree to which STAGE-12 increases involvement in 12-step activities and attendance at 12-step meetings, and the extent to which such 12-step involvement and meeting attendance mediate substance use outcomes.

STUDY DESIGN: This is a randomized, 2-group design comparing STAGE-12 integrated into TAU (STAGE-12) to TAU without STAGE-12 (TAU) for stimulant abusers receiving formal substance abuse treatment in participating community-based treatment programs (CTPs). For the purposes of this study, the STAGE-12 sessions will replace 8 sessions (3 individual and 5 group sessions) from TAU during the course of the intervention period, which may range from 5 up to 8 weeks. Eligible, consented stimulant abusers entering treatment at participating CTPs will be assigned randomly within site through a centralized randomization procedure to STAGE-12 or TAU and will be stratified by participants' court-mandated for treatment versus not court-mandated. Assessments will be conducted as indicated in Table 1 at baseline, weeks 2, 4, and 8. Follow-up assessment will occur at 3 and 6 months after randomization.

STUDY POPULATION: A total of approximately 400 stimulant users seeking formal treatment, recruited from approximately 10 CTPs, will be randomized to STAGE-12 or TAU. Each CTP will enroll approximately 40-50 participants, with a target of 20-25 per CTP in each treatment condition. Eligible CTPs and counselors will be assessed to characterize their general treatment philosophy/orientation.

ELIGIBILITY CRITERIA: Participants will be individuals 18 years of age or older who are seeking outpatient treatment for stimulant abuse or dependence, have used stimulants over the previous 60 days, have a current diagnosis of stimulant abuse or dependence, and are willing to participate in the protocol (e.g., to be randomized to treatment, be contacted for follow-up assessment, to have their sessions audio-taped). Individuals who are not sufficiently medically or psychiatrically stable to participate in outpatient treatment will be excluded. Individuals who have pending legal actions that would inhibit their participation in the study, or who, in the clinical judgment of CTP staff, are in need of detoxification from opiates will also be ineligible.

TREATMENTS: The STAGE-12 intervention will consist of a combination of five group and three individual sessions. The five group sessions will be taken from the Project MATCH Twelve Step Facilitation manual as modified for use with drug abusers (Baker 1998; Carroll, Nich et al. 1998) and adapted for delivery in a group format (Brown, Seraganian et al. 2002; Brown, Seraganian et al. 2002). The group sessions will be augmented by three individual sessions derived from the introductory and termination sessions from the TSF manual and incorporating elements of the brief intensive 12-step referral procedure developed by Timko and colleagues (Timko, DeBenedetti et al. 2006). The group and individual sessions focus on increasing both understanding 12-step principles and attending 12-step meetings and engaging in 12-step activities. The Twelve-Step Facilitation (TSF)-based group sessions utilize those sessions defined as "core" topics. These focus on the principles of Steps 1–3, such as surrender and acceptance, as well as changing one's lifestyle and getting active in 12-step programs. The individual sessions focus on and reinforce the theme of getting active in 12-step and facilitate this by arranging for participants to connect with

volunteers from a local 12-step group who will take them to a meeting and serve as a temporary sponsor. The group and individual sessions thus complement each other. The STAGE-12 group sessions emphasize the need to gain an understanding and acceptance of the concepts and principles of 12-step philosophy. Correspondingly, the intensive referral intervention emphasizes and facilitates getting actively involved, through behaviors such as attending 12-step meetings, reading 12-step literature, and getting a sponsor. Participants assigned to the TAU condition will be offered the treatment typically provided by the CTP, which may include more passive procedures for referring clients to 12-step meetings. Counselors selected to deliver the STAGE-12 intervention will be chosen randomly from a pool of eligible counselors within CTPs who volunteer to participate.

SAFETY ASSESSMENT: All participants will provide informed consent prior to their involvement in the protocol. There will be ongoing monitoring of adverse events, with participants having an opportunity at each research visit point to indicate whether they have experienced any adverse events.

OUTCOME ASSESSMENTS: The primary outcome measure will be percent of days of stimulant use based on a substance use calendar. Secondary substance use outcome measures will include percent of days of use of drugs other than stimulants, urine toxicology results, and ASI Alcohol and Drug Composite scores. Additional secondary outcomes will include measures of involvement in 12-step activities (e.g. reading 12-step literature, helping set up for a meeting, getting a sponsor), 12-step meeting attendance, and 12-step beliefs. These primary and secondary measures will be collected as indicated in Table 1.

ANALYSIS: The primary and secondary outcome variables will be analyzed using appropriate statistical methods for an intent-to-treat (ITT) population.

REGULATORY ISSUES: The trial will be conducted in compliance with protocol, ICH Good Clinical Practice (GCP) guidelines, and applicable regulatory requirements.

Obtain Written Informed Consent from Eligible Participants Conduct Screening and Baseline Assessments All Eligibility Criteria Met Assign to Intervention Using Centralized Randomization **Scheduled Assessments Scheduled Assessments** and Treatment as Usual and STAGE-12 Integrated Without STAGE-12 into Treatment as Usual -(TAU) (STAGE-12) **Conduct End of Intervention Assessment at** Week 8 **Conduct 3-month Post-Randomization** Assessment **Conduct 6-month Post- Randomization Assessment**

Figure 1: STAGE-12 Protocol Study Schema

3.0 BACKGROUND AND SIGNIFICANCE

3.1 Role of 12-Step Self-Help Groups in Substance Abuse Treatment and Recovery

Twelve-step and mutual/self-help groups represent an important, readily available, and pervasive resource in substance abuse recovery, whether associated with formal treatment or not (Room and Greenfield 1993; Humphreys 1999; Kelly 2003). Substance abusers can become involved with 12step groups before entering professional treatment, as part of their professional treatment, as aftercare following professional treatment, or instead of professional treatment (Fuller and Hiller-Sturmhofel 1999). These groups, which include Alcoholics Anonymous (AA), Narcotics Anonymous (NA), Cocaine Anonymous (CA), Crystal Meth Anonymous (CMA) and a number of others, are highly accessible and are available at no cost in communities throughout the world. For some substance abusers, these meetings are the only resource ever used to resolve a drinking or drug problem (Room and Greenfield 1993; Hasin and Grant 1995; Kaskutas, Weisner et al. 1997). The 12-Step philosophy has had a strong influence on the evolution of formal alcoholism treatment in the United States, primarily in the form of the Minnesota Model (Alford, Koehler et al. 1991; McElrath 1997; Stinchfield and Owen 1998). Although initiated with alcohol as its primary focus, this philosophy has also been integrated into the treatment of drug dependence, as in the Group Drug Counseling (GDC) and Individual Drug Counseling (IDC) approaches developed for treatment of cocaine addicts (Crits-Christoph, Siqueland et al. 1997; Crits-Christoph, Siqueland et al. 1999; Daley, Mercer et al. 1999; Mercer and Woody 1999). Participation in 12-step groups is also a recommended component in the Matrix Model used in the treatment of both cocaine and methamphetamine dependence (Shoptaw, Rawson et al. 1994; Rawson, Shoptaw et al. 1995; Obert, McCann et al. 2000). Many residential and outpatient substance abuse treatment programs include 12-step meetings on-site and encourage clients to become involved in community-based 12-step meetings and activities (Fuller and Hiller-Sturmhofel 1999).

The 12-step philosophy refers to a particular view of the recovery process. It emphasizes the importance of accepting addiction as a disease that can be arrested but never eliminated, enhancing individual maturity and spiritual growth, minimizing self-centeredness, and providing help to other addicted individuals (e.g., sharing recovery stories in group meetings, sponsoring new members) (Humphreys, Wing et al. 2004). Self-help groups based on this philosophy outline 12 consecutive activities, or steps, that substance abusers should achieve during the recovery process. These steps specify that substance abusers must admit their powerlessness over alcohol and drugs, take a moral inventory of themselves, admit the nature of their wrongs, make a list of individuals whom they have harmed, and make amends to those people. Involvement in such groups is meant to provide participants with support for remaining substance free, a social network (the "fellowship") with which to affiliate, and a set of 12 guiding principles (the "steps") to be followed in the recovery process (Kaskutas, Bond et al. 2002). Caldwell and Cutter (Caldwell and Cutter 1998) described the general guidelines for recovery based on this philosophy as the "12-step'six pack:" don't drink or use drugs, go to meetings, ask for help, get a sponsor, join a group, and get active.

3.2 Effectiveness / Efficacy of 12-Step Self-Help Groups

There has been an increased focus on 12-step self-help groups by clinicians, policy makers, and researchers over the recent past. Humphreys (Humphreys 1999) suggests that fiscal factors and

developments in clinical research have contributed to this increased attention. First, given recent cutbacks in funding for professional substance abuse treatment, 12-step groups are seen as an inexpensive and readily available complement to formal treatment and as a source of support following treatment (Etheridge, Craddock et al. 1999; Fiorentine 1999; Humphreys 1999; Humphreys 2003). Secondly, until recently there have been few well-controlled studies supporting the clinical effectiveness of 12-step approaches (Tonigan, Toscova et al. 1996). However, more recent efficacy and effectiveness trials provide support for the effectiveness of 12-step oriented approaches (Donovan 1999). Generally, these studies have found a positive relationship between 12-step involvement and improvement on substance use outcomes for both alcoholics and drug abusers, even over extended periods of time ranging up to 16 years (Emrick, Tonigan et al. 1993; Montgomery, Miller et al. 1995; Timko, Finney et al. 1995; Morgenstern, Labouvie et al. 1997; Project Match Research Group 1997; Watson et al., 1997; Ouimette, Moos et al. 1998; Fiorentine and Hillhouse 2000; Fiorentine and Hillhouse 2000; Weiss, Griffin et al. 2000; McKay, Merikle et al. 2001; Tonigan 2001; Kaskutas, Bond et al. 2002; Morgenstern, Bux et al. 2003; Moos and Moos 2004; Kaskutas, Ammon et al. 2005; Moos and Moos 2005; Moos and Moos 2006).

While the positive relationship between 12-step involvement and clinical outcomes is encouraging, it is not possible to infer a causal relationship from correlational findings. Three recent studies, using cross-lagged analyses of longitudinal data or structural equation modeling, have begun to elucidate the nature of this relationship. Connors, Tonigan, Miller, and the Project MATCH Research Group (Connors, Tonigan et al. 2001) found that a construct of intake symptomatology (i.e., severity of alcohol dependence, alcohol involvement, psychiatric severity, and readiness to change) predicted AA involvement (which included both meeting attendance and activities) during the first 6 months following treatment. Further, AA involvement during the first 6 months post-treatment predicted drinking outcomes during months 7-12. Drinking outcomes, however, were not predicted by intake symptomatology. This latter result helped rule out a competing hypothesis that the relationship between AA involvement and clinical outcome might rather be due to a more global construct of "good prognosis."

McKellar, Stewart, and Humphreys (McKellar, Stewart et al. 2003) examined the predictive utility of a latent variable, AA involvement, in a structural equation model (SEM). Latent variables in SEM are hypothetical constructs that are defined by directly measured indicator variables. Four indicators defined the AA Involvement latent variable. These indicator variables, each rated on a 5-point scale with respect to the immediately preceding 3-month time frame, were: (1) number of AA meetings attended, (2) frequency of reading AA books and/or pamphlets, (3) frequency of talking to one's AA sponsor, and (4) and the number of AA friends. The AA Involvement construct, assessed in the first year post treatment, predicted reduced drinking and alcohol-related problems in year 2. However, the level of drinking and alcohol-related problems in year 1 did not predict 12-step attendance or involvement in year 2. Two studies (Connors, Tonigan et al. 2001; McKellar, Stewart et al. 2003) controlled for levels of readiness to change, thus removing differential motivation across subjects as an explanatory factor.

Weiss et al. (Weiss, Griffin et al. 2001; Weiss, Griffin et al. 2005), in a cross-lagged analysis, found that self-help meeting attendance by individuals being treated for cocaine dependence did not predict subsequent drug use. However, active involvement in self-help activities (as opposed to meeting attendance) in a given month predicted fewer days of cocaine use in the next month. Moreover, patients who increased their involvement in self-help activities during the first three months of treatment had significantly fewer days of subsequent cocaine use and lower scores on the Addiction Severity Index (ASI) Drug Use Composite in the subsequent 3 months. Further, the best outcomes were found among those individuals who both received the 12-step oriented Individual Drug Counseling (IDC) and increased their 12-step participation in months 1-3, while

patients who neither received IDC nor increased their participation had the worst outcomes. Individuals who received IDC but did not increase their participation and those who did not receive IDC but did increase their participation had outcomes that were intermediate between these other two groups. Thus, the combined effects of being involved in a treatment approach that emphasizes 12-step involvement plus actual engagement in self-help activities was associated with the best outcomes, better than those found with either of these alone.

The conclusion drawn by McKellar, et al. (McKellar, Stewart et al. 2003) applies equally well to the results of Connors, et al. (Connors, Tonigan et al. 2001), and Weiss, et al. (Weiss, Griffin et al. 2001; Weiss, Griffin et al. 2005): "The current study increases confidence in the effectiveness of AA (and other 12-step self-help groups) by using multi-wave longitudinal data and by accounting for potential third variable influences such as motivation and psychopathology" (p. 307). These data provide increasingly supportive evidence for the hypothesis that 12-step involvement "works;" that is; increased 12-step meeting attendance and/or involvement appear to lead to a decrease in subsequent alcohol and drug use. Attendance at 12-step meetings, whether independent of formal treatment or as an adjunct to treatment, has also been found to be associated with reductions in health care costs, particularly those related to subsequent substance abuse treatment (Humphreys and Moos 1996; Humphreys and Moos 2001). Further, treatment approaches or interventions that are meant to increase engagement appear to be effective in doing so and, thus, contributing to positive substance use outcomes through their impact on increasing 12-step activities and attendance (Carroll, Nich et al. 1998; Humphreys 1999; Morgenstern, Bux et al. 2003; Weiss, Griffin et al. 2005).

3.3 12-Step Meeting Attendance and Engagement in 12-Step Activities

McKellar, et al. (McKellar, Stewart et al. 2003) questioned whether measures of meeting attendance alone would predict the same substance use outcomes and to the same extent as involvement in 12-step practices and activities (e.g., reading 12-step literature, getting a sponsor, "working" the steps, or helping set up meetings). These two variables, though related, appear to have different relationships with subsequent substance use (Weiss, Griffin et al. 2005). Involvement, rather than attendance, appears to be the better predictor of substance use outcomes: the greater the level of involvement in 12-step activities, the better the outcome. This has been found for both alcoholics (Gilbert 1991; Montgomery, Miller et al. 1995; Caldwell and Cutter 1998) and cocaine abusers (Weiss, Griffin et al. 2000; Weiss, Griffin et al. 2001; Weiss, Griffin et al. 2005). As Emrick, et al. (Emrick, Tonigan et al. 1993) concluded, "mere attendance at meetings may, in fact, be a fairly weak indicator of commitment" (p.63). Tonigan, Connors, and Miller (Tonigan, Connors et al. 1996) note that measures of 12-step attendance are likely to overestimate the extent of 12-step engagement: More people are attending than are getting involved in the program. However, regular attendance may be a precursor for involvement for many. Caldwell and Cutter (Caldwell and Cutter 1998) found that individuals who attend AA daily in early recovery are more likely to embrace both the program and fellowship dimensions of AA, and that those who have dropped out or who attend meetings infrequently or erratically tend to be less accepting of all aspects of AA. This latter group also appears to do less well than those who have frequent and consistent attendance (Morgenstern, Kahler et al. 1996; Weiss, Griffin et al. 2000; Moos and Moos 2004; Kaskutas, Ammon et al. 2005; Moos and Moos 2005). Fiorentine (Fiorentine 1999) found that weekly or more frequent meeting attendance was associated with drug and alcohol abstinence among clients at outpatient drug treatment programs. Similarly, Moos (Moos and Moos 2004) found that more frequent participation in AA (e.g., attending two or more meetings per week) during the first year after seeking help was associated with a higher likelihood of subsequent abstinence at 1- and 8-year follow-ups. Furthermore, the timing of this attendance was crucial. Early involvement was important; individuals who delayed participation for a year or more and then eventually entered AA had outcomes that were no better than those of individuals who never entered AA. Continued attendance and the duration of involvement in 12-step activities over time were also important and were predictive of a broader range of substance use and psychosocial outcomes than was attendance. Finally, participation in AA had a positive influence on alcohol-related outcomes over and above the effects attributable to professional treatment, which is consistent with the findings of Fiorentine and Hillhouse (Fiorentine and Hillhouse 2000) with drug abusers.

A clinical implication of these findings is that it is important not only to get substance abusers to attend 12-step meetings, but to do so early after they have sought treatment and to encourage consistent attendance over time. It is also important to have substance abusers become actively involved in the 12-step process beyond meeting attendance. However, interventions that are effective in increasing attendance may be insufficient to ensure active involvement. Caldwell and Cutter (Caldwell and Cutter 1998) suggest that individuals who are attending AA but are having difficulty embracing key aspects of the program may need professional assistance that focuses more on 12-step practices and tenets and less on meeting attendance.

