5.4.3.4.3 Stages of Change Readiness and Treatment Eagerness Scale (SOCRATES)

The SOCRATES (Miller and Tonigan 1996) is a 20-item self-report measure of clients' readiness to change their substance use behaviors. It will be administered at the baseline and End of Treatment/week 8 visits. Originally, the 40-item scale had five subscales based on Prochaska and DiClemente's Stages of Change model of addictive behaviors. The SOCRATES was developed and its psychometric properties determined in Project MATCH. Isenhardt (Isenhart 1994) has used a modified version of the SOCRATES that includes references to drug use with a broader range of substance abusers; this is the version that will be employed. The current version has three subscales: Taking steps, Recognition of a problem, and Ambivalence. The instrument is intended to assess which of these stages the individual is in at the time of the assessment. Psychometric properties of the SOCRATES are good to excellent. Cronbach's alpha for the three scales ranged from .88 to .96, while test-retest reliability ranged from .83 to .99. The final three-factor solution seems stable. Inclusion of a measure of readiness to change is important in light of the findings by Laudet (Laudet 2003). Major obstacles to participation in 12-step programs centered on motivation and readiness for change and on perceived need for help, rather than on aspects of the 12-step program often cited as points of resistance (e.g., religious aspect and emphasis on powerlessness).

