10.3 Primary Outcomes

10.3.1 Hierarchical linear model

The primary outcome variable will be percent of days of stimulant use over the assessment window, based on Substance Use Calendar alone and assessed at baseline, weeks 4 and 8/end of treatment, 3 months and 6 months. This measure will be analyzed using hierarchical linear models. Specifically, the trajectory over time for an individual patient will be described by the Level-1 model

(1)
$$Y_{ijk} = X_i \varphi + \beta_{0ij} + \beta_{ij} t_{ik} + \varepsilon_{ijk}, \qquad k=1,..., n_i$$

where Y_{ijk} and ε_{ijk} are percent of days of stimulant use and error term of participant i at site j at post-baseline assessment k, β_{0ij} is the baseline percent of stimulant use, β_{ij} is the slope for participant i, t_{ik} is the number of weeks at post-baseline assessment k, n_i is the number of post-baseline assessments for participant i, which can differ between the participants reflecting attrition; X_i is a baseline variable describing whether participant i was court mandated for treatment ($X_i = 1$) vs. not court-mandated for treatment ($X_i = 0$).

The Level-2 model describes the slope for participant *i* as a function of the treatment arm:

(2)
$$\beta_{ii} = \alpha_{0i} + \alpha_1 I(STAGE-12) + b_{ii}$$

Here α_{0j} is the intercept for participants at the *j*th treatment site, α_1 is the effect of the STAGE-12 treatment, *I*(STAGE-12) is a 0-1 STAGE-12 treatment indicator and b_{ij} is a subject-specific random error term.

The Level-2 model also describes the baseline outcome measure for participant i:

$$\beta_{0ij} = \alpha_{00j} + b_{0ij}$$

Here α_{00j} is the intercept for participants at the *j*th treatment site and b_{0ij} is a subject-specific random error term.

The assumptions of the model are: a) $\mathbf{e}_{ij} = (\varepsilon_{ij1},...,\varepsilon_{ijn_i})^T$ are independent $N(0,\Sigma_i)$ where Σ_i depends in i only through its dimension, b) b_{ij} are independent $N(0, \sigma_b^2)$, uncorrelated with ε_{ijk} , c) b_{0ij} are independent $N(0, \sigma_0^2)$, uncorrelated with b_{ii} and ε_{ijk}

The primary analysis will evaluate the hypotheses H_0 : $\alpha_1 = 0$ vs. H_1 : $\alpha_1 \neq 0$ and rejection of the null hypothesis with $\alpha_1 < 0$ would indicate that STAGE-12 treatment reduces percent of days of substance use compared to TAU.

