10.4.3.1.1 Hypothesis

Reductions in substance use, regardless of treatment condition, are mediated by increases in 12-step attendance and 12-step activities.

The outcome variable will be percent of days of substance use over the assessment window, based on Substance Use Calendar alone and assessed at baseline, weeks 4, 8/end of treatment, 3 months and 6 months. The hypothesis will be investigated by adding an interaction term time*Mediator to the hierarchical linear model for the primary outcome, where Mediator denotes the factor of interest (12-step attendance or 12-step activities). Let γ_M denote the model coefficient associated with the time*Mediator term. The hypothesis H_0 : γ_M =0 vs. H_1 : $\gamma_M \neq 0$ will be evaluated and rejection of the null hypothesis with γ_M < 0 would indicate that increases in 12-step attendance (12-step activities) result in reduction in substance use, regardless of treatment condition.

Objective: To examine client attitudes and beliefs as mediators of 12-step meeting attendance and involvement.

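### The mediation test in 10.4.3.1.1 leaves out baseline readiness to change and psychiatric severity, both collected and both expected to predict attendance, yet reads the coefficient causally

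*Protocol*

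**What the plan says.** The mediation analysis is set out in Protocol 10.4.3.1.1: "The hypothesis will be investigated by adding an interaction term time*Mediator to the hierarchical linear model for the primary outcome". The mediator is named only as the factor of interest, either 12-step attendance or 12-step activities. A negative coefficient γ_M "would indicate that increases in 12-step attendance (12-step activities) result in reduction in substance use, regardless of treatment condition".

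The primary model (10.3.1) contains site-specific intercepts and time slopes, the arm-by-time effect, subject-level random terms and one person-level covariate X, which "is a baseline variable describing whether participant" i was court-mandated. No other baseline characteristic is in it.

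The protocol treats motivation and psychiatric severity as relevant in several other places:

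- Section 3.2 warns that "it is not possible to infer a causal relationship from correlational findings". It values two earlier studies because they "controlled for levels of readiness to change, thus removing differential motivation across subjects as an explanatory factor", and it repeats a conclusion that rests on "accounting for potential third variable influences such as motivation and psychopathology".
- Section 5.4.3.4.3 justifies collecting SOCRATES on the ground that "Major obstacles to participation in 12-step programs centered on motivation and readiness for change". SOCRATES is given at baseline and week 8.
- Section 5.4.3.1.3 has the ASI-Lite given at baseline and assigns its psychiatric composite the role of a predictor.
- Sections 10.4.4.1.3 and 10.4.4.1.5 hypothesise that higher psychiatric severity goes with less, and higher readiness with more, meeting attendance and 12-step activity.

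On status, 5.4.3 calls the mediation analyses exploratory. Section 10.4 makes no multiplicity adjustment and treats significant secondary findings as exploratory. Mediation is nonetheless a listed secondary objective in 2.0 and 4.2.

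**The concern.** Arm is randomised; attendance is not. A participant who is readier to change may attend more meetings and, separately, use fewer stimulants. In that case γ_M is negative even if attendance does nothing. The random intercept and slope do not protect against this, because the model takes them as independent of its covariates, the mediator included.

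This is the alternative explanation that section 3.2 credits earlier studies for addressing. The trial collects the two baseline measures needed to address it, but the stated model uses neither. The stated rule then turns the unadjusted coefficient into a claim about what attendance does. At stake is a secondary conclusion that would rest on weaker control than the work it is meant to extend.

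**Working it through.** **No figure to reproduce.** The protocol gives no number for the mediation analysis. The check has two parts: reading the model, and illustrating size under assumptions.

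**Part 1: terms in the model against variables available.**

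| Variable | Measured at baseline | Expected to predict attendance | In the 10.4.3.1.1 model |
|---|---|---|---|
| Court mandate | yes | not stated | yes (10.3.1) |
| Readiness to change (SOCRATES) | yes (5.4.3.4.3) | yes (10.4.4.1.5) | no |
| Psychiatric severity (ASI) | yes (5.4.3.1.3) | yes (10.4.4.1.3) | no |

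**Part 2: size if the omitted trait also affects use.** In every calculation the true mediator effect is zero. The test is two-sided at 0.05, so the nominal rate for γ_M < 0 is 2.5%. The strength of confounding is assumed, because the documents give none.

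*(a) Analytic upper end.* Let one baseline trait correlate q with both the mediator and the outcome slope. The spurious correlation is r = q × q, and the chance of a significant result in the negative direction is about Φ(√(N − 3) · atanh(r) − 1.96). For q = 0.3 and N = 400: r = 0.09, √397 × atanh(0.09) = 1.80, and Φ(1.80 − 1.96) = 43.6%.

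| q | N = 400 | N = 280 (70% of 400) |
|---|---|---|
| 0.1 | 3.9% | 3.6% |
| 0.2 | 12.3% | 9.8% |
| 0.3 | 43.6% | 32.3% |
| 0.4 | 89.5% | 76.6% |

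These are upper-end values, because slopes are treated as measured without error.

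*(b) Noisy slopes.* Each person's slope was estimated from weeks 4, 8, 13 and 26, with 70% completers of 400, assumed variances and 4000 runs. Rejection with γ_M < 0 was 4.9% (q = 0.2), 9.9% (0.3), 21.0% (0.4) and 44.8% (0.5). With the trait added, two-sided rejection was 4.3% to 5.6% for q from 0 to 0.5, against a nominal 5%.

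*(c) Section 10.6 assumptions.* The inputs were 400 participants, SD 23.7, compound symmetry with ρ = 0.5, even dropout to 70% and 800 trials per setting. The trait's correlation with the mediator was set at 0.3 or 0.5, and its effect on month-6 use at 3, 5 or 7 points per SD. The mediator entered as a level. Rejection with γ_M < 0, without and with trait-by-time:

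| Effect on use (points per SD) | Correlation 0.3 | Correlation 0.5 |
|---|---|---|
| 3 | 8% / 2% | 18% / 3% |
| 5 | 19% / 2% | 41% / 3% |
| 7 | 31% / 3% | 65% / 3% |

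A run of the same scenario that added literally only the time-by-mediator term gave 12% to 79% unadjusted and 1.5% to 2.9% adjusted. The unadjusted rates are higher when the mediator has no main effect in the model.

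*(d) Weak or no confounding.* In the same scenario, an effect on use of 0 gave about 2%, and 1 point per SD gave about 4%.

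*(e) Mediator as change from baseline.* If the trait shifts attendance equally at every visit, it cancels from a change score. False support was then 2% to 4% for effects from 0 to 7 points at both correlations.

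**The case against.** **The link from these traits to drug use is not in the documents.** A reader might infer that the protocol itself makes readiness a common cause of attendance and use. It supports only the first half. On the second half, section 3.2 points the other way: in one cited alcohol study, an intake construct that included psychiatric severity and readiness did not predict drinking, and this was taken as evidence against a good-prognosis explanation. This stands, and the size of any confounding here is unknown. It does not remove the concern. That construct also mixed in dependence severity and alcohol involvement, the outcome was drinking rather than stimulant use, and the same section still credits control for readiness.

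**The background does not demand adjustment.** A reader might take section 3.2 to say these variables must be controlled. It credits studies that did so and sets no requirement.

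**The simulated range is chosen.** Effects of 3 to 7 points per SD have no source in the documents and leave out zero. Seven points is large beside the 10-point between-treatment difference that 10.6 calls clinically meaningful. Recovery after adjustment is partly by construction: there is one confounder, measured perfectly, and psychiatric severity is not simulated separately. All of this stands.

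**A change-score mediator could avoid the problem.** The hypothesis speaks of increases, and attendance is measured at baseline. Under (e) the inflation disappears, so it would be wrong to say that confounding persists however the mediator is built. But 10.4.3.1.1 does not define the mediator as a change, and the cancellation needs its own assumption.

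**Exploratory status and the unseen SAP.** The exploratory label is a fair limit on importance. The SAP argument is weaker, because the protocol itself fixes the model, the test and the interpretation.

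**Conclusion.** The point holds in a limited form. As written, 10.4.3.1.1 omits two baseline variables that the protocol collects, expects to predict attendance, and regards as worth controlling in earlier work; it then gives the coefficient a causal reading.

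The size is conditional. If readiness and psychiatric severity have little effect on stimulant use, false support stays near the nominal 2.5% (about 2% to 4% in (d)). Under assumed moderate to strong confounding, with the mediator entered as a level, it is roughly 10% to 65% or more.

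A reader might go further and conclude that the efficacy result is compromised, or that the same defect is shown for 10.4.3.1.2 to 10.4.3.1.4. Neither follows. The primary test of α₁ does not involve the mediator. The later hypotheses have other outcomes and mediators, their stated test (in 10.4.3.1.4) carries no causal reading, and they were not examined here. The change is worth making because it is cheap, even though the analysis is exploratory.

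**What to change.** In 10.4.3.1.1:

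1. Add the baseline SOCRATES subscales and the baseline ASI Psychiatric composite to the model, each as a main effect and by time.
2. Base the mediation statement on the adjusted coefficient.
3. Replace *result in* with *are associated with* in the interpretation. Adjustment does not remove unmeasured confounding, nor the fact that mediator and outcome are measured concurrently.

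The cost is a few degrees of freedom and a mediator estimate that will probably be smaller. No data, visits or participants are added.
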